### 10.1.1 Reporting of SAEs

All SAEs must be reported immediately and within a maximum of 24 hours to the Sponsor-Investigator of the study. The Sponsor-Investigator will re-evaluate the SAE and return the form to the site.

SAEs resulting in death are reported to the local Ethics Committee (via local Investigator) within 7 days. The other in the trial involved Ethics Committees receive SAEs resulting in death in Switzerland via Sponsor-Investigator within 7 days using the BASEC account.

Exemptions from expedited reporting may be possible if the SAE is either a clear result of the underlying disease or well-known and described in the currently approved product information.

### 10.1.2 Reporting of SUSARs

A SUSAR needs to be reported to the local Ethics Committee (via Sponsor-Investigator in Switzerland using BASEC) and to Swissmedic (via Sponsor-Investigator) within 7 days, if the event is fatal, or within 15 days (all other events).

The Sponsor-Investigator will inform all Investigators participating in the clinical study of the occurrence of a SUSAR. All in the trial involved Ethics Committees will be informed about SUSARs in Switzerland via Sponsor-Investigator according to the same timelines.

## 11. STATISTICAL METHODS

A detailed Statistical Analysis Plan will be drawn up before breaking the randomisation code.

### 11.1 Hypothesis

The null hypothesis (H0) is that tranexamic acid does not alter HE in participants with acute NOAC-ICH. The alternative hypothesis (HA) is that HE differs between those participants randomised to tranexamic acid versus placebo.

### 11.2 Determination of Sample Size

There exists no retrospective or prospective study reporting rates of HE in NOAC-ICH. Based on the largest available studies investigating HE in anticoagulation-related ICH ranging from 54-56% in VKA-ICH we estimate a 54% rate of HE in placebo NOAC-ICH patients.

As there are no previous trial data on the effect of TA in NOAC-ICH, we base our sample size estimate on feasible recruitment rates and use an adaptive sample size procedure as done in prior research. Estimating a rate of 27% of HE in NOAC-ICH patients receiving TA, we provisionally plan our sample size at 109 patients. This yields 80% power to detect a significant absolute difference in the proportion of patients with hematoma enlargement at 24 h at a two-sided statistical significance threshold of  $P = 0.05$ .

Justified by lack of previous efficacy data, adaptive increase in sample size is planned. An interim analysis of the primary endpoint is performed using data from the first 82 patients. As described in Mehta & Pocock the sample size is increased if and only if the results of the interim analysis are 'promising' (i.e. power is in the predefined 'promising' range). In the interim analysis conditional power is evaluated and if it falls within the prespecified 'promising' range between 0.33 - 0.8, the sample size will be increased to increase the conditional power to 0.8 level, but at most to the predetermined upper limit of 218 patients. With a sample size of 218 patients, the trial should detect with 80% power an incidence rate in relevant hematoma expansion under TA of 35 % assumed a drop-out rate of 5 % and an incidence rate of 54 % under placebo. If the estimated sample size exceeds 218, continuation of the trial will be discussed with the CIs and the steering committee. The final decision to increase the sample size or stop the trial prematurely will be taken by the CIs and the steering committee.

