### 11.3 Statistical criteria of termination of trial

The DSMC will recommend to the TSC that the trial be stopped if there is proof beyond reasonable doubt (with a 99% CI) of overall benefit with the active treatment or if there is a lower level of evidence suggesting overall hazard. Evidence of hazard will include effect on the primary outcome (HE) and analysis of safety endpoints, as specified in the protocol (death, VTE, ischaemic events, seizures, serious adverse events).

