### **12.2 Monitoring**

During the course of the trial the Data Safety and Monitoring Board (DSMB) will after recruitment of 50% and 80% of the trial population perform an review of SAEs, in all patients; in case of concerns, unblinding will be requested. If, in their view, there is credible evidence of harm, or overwhelming evidence of efficacy, the committee will advise the CIs. Unless this happens, the CIs and the Steering Committee will remain ignorant of all interim results.

The DSMB will also be responsible for monitoring the overall conduct of the trial, and may formulate recommendations relating to the selection, recruitment, or retention of participants, or their management, or to improving their adherence to protocol-specified regimens, and the procedures for data management and quality control.

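### After the 82-patient interim analysis, Section 11.2 has the CIs and steering committee decide whether to enlarge or stop the trial, while Section 12.2 withholds from them the result on which they would decide

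*Combined protocol and SAP*

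**What the plan says.** Section 11.2 plans 109 patients and an interim analysis of the primary endpoint in the first 82. The rule is worded as binding: "the sample size is increased if and only if the results of the interim analysis are" promising, meaning conditional power between 0.33 and 0.8. The size is then raised to bring conditional power to 0.8, "but at most to the predetermined upper limit of 218 patients". Two further sentences follow: "If the estimated sample size exceeds 218, continuation of the trial will be discussed with the CIs and the steering committee", and "The final decision to increase the sample size or stop the trial prematurely will be taken by the CIs and the steering committee".

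Section 12.2 describes DSMB reviews of serious adverse events at 50% and 80% recruitment, where "in case of concerns, unblinding will be requested". The board advises the CIs if it sees credible harm or overwhelming efficacy. Then: "Unless this happens, the CIs and the Steering Committee will remain ignorant of all interim results".

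Section 11.3 gives the board a stopping role that includes efficacy: "The DSMC will recommend to the TSC that the trial be stopped if there is proof beyond reasonable doubt (with a 99% CI". It also counts the effect on haematoma expansion as evidence of hazard. It mentions neither conditional power nor sample size. The recipient of the board's advice varies: the chief investigator (1.6), the TSC (1.7 and 11.3) or the CIs (12.2).

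**The concern.** Conditional power for haematoma expansion cannot be computed without the results by arm, so the 82-patient analysis is unblinded. Section 11.2 hands the resulting decision to the bodies that Section 12.2 shields from interim results. The only exceptions in 12.2 are harm and overwhelming efficacy, and conditional power of 0.33 to 0.8 is neither.

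Two things are at stake. First, with no stated channel, the people running the trial may learn the approximate effect on haematoma expansion while patients are still being enrolled, which Section 12.2 is meant to prevent. Second, if the increase is optional, the design's operating characteristics are undefined, because they depend on how the committees would use their discretion.

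**Working it through.** **The plan's own figures.** For 54% versus 27%, two-sided 0.05, 80% power, 1:1 and pooled variance, the requirement is 51 per arm, 102 in total. With 5% drop-out, 102/0.95 = 107.4, or 108 in even numbers, close to the stated 109. (The 5% is stated only for 218, so using it here is an assumption.) For 54% versus 35%, 218 × 0.95 = 207 patients give power 0.79 against the stated 80%. The sizes are not in dispute.

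**The passages side by side.**

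| Question | Section 11.2 | Section 12.2 |
|---|---|---|
| Who acts on a promising result? | CIs and steering committee | Same bodies, kept ignorant of it |
| Is the increase binding? | Yes by the rule; no by the decision sentence read broadly | Silent |
| Required size above 218, in the zone | Cap at 218, and also discuss continuation | Silent |
| Who computes conditional power? | Not stated | Not stated; describes a safety review |

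**How often it matters.** The plan gives no conditional-power formula, so what follows is illustrative. Assumptions: observed-trend conditional power, interim at 82, planned size 109, critical value 1.96, zone in the benefit direction only, unadjusted pooled-variance Z, normal approximation, no drop-out, no other looks.

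CP(Z) = 1 − Φ[(1.96√109 − Z√82)/√27 − Z√27/√82]

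- Lower limit, Z = 1.510: (20.463 − 13.674)/5.196 − 0.867 = 0.440, so CP = 0.33.
- Upper limit, Z = 2.063: (20.463 − 18.681)/5.196 − 1.184 = −0.841, so CP = 0.80.
- Difference in rates = Z√(4p(1−p)/82). With an assumed pooled rate p of 0.40 to 0.45, the zone runs from about 16 points (1.510 × 0.108) to 23 points (2.063 × 0.110).
- Mean interim Z at 54% versus 27%: 0.27/0.1084 = 2.490. P(zone) = Φ(−0.427) − Φ(−0.980) = 0.171.
- Mean interim Z at 54% versus 35%: 0.19/0.1098 = 1.731. P(zone) = Φ(0.332) − Φ(−0.221) = 0.218.

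**Cap versus discussion.** The required size reaches 218 at Z = 1.577 if the conditional critical value from 109 is kept, or at Z = 1.610 with the conventional test at the new size. Between Z = 1.510 and those values both sentences apply: 1.7% to 2.6% of trials at 54% versus 27%, and 2.6% to 3.9% at 54% versus 35%.

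**Cost of discretion** (ranges cover the two formulas for required size):

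| | 54% vs 27% | 54% vs 35% |
|---|---|---|
| Power, rule followed | 0.850–0.853 | 0.558–0.563 |
| Power, trial stopped only in the overlap | 0.828–0.833 | 0.530–0.536 |
| Power, every increase declined | 0.819 | 0.514 |

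Declining every increase therefore costs 3.1 to 3.4 points and 4.4 to 4.9 points. Two-sided type I error under the rule is about 0.049. Staying at 109 or stopping does not raise it above 0.05.

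**What a released size reveals.** Below the cap, size maps one-to-one to Z. A target of 150 means Z of 1.80 or 1.87, depending on the formula: 1.80 × 0.108 = 0.19 to 1.87 × 0.110 = 0.21, or about 20 points.

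**Timing.** 82/109 = 75.2%. The DSMB meetings fall at about 55 (0.50 × 109) and 87 (0.80 × 109) recruited, so neither is the 82-patient analysis.

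**The case against.** The strongest reply is that the final-decision sentence directly follows the sentence on estimates above 218 and may concern only that case: increase to the cap, or stop. The mandatory rule and the discretion then form one procedure, and inside the zone discretion arises in only 1.7% to 3.9% of trials. This reading is coherent and largely dissolves the conflict within Section 11.2. It is not compelled, because the sentence carries no such limit. Nor does it remove the conflict with Section 12.2: the committees would still act on an interim result withheld from them.

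A second reply is that they could act on a bare board recommendation. Sections 1.7, 2.9 and 11.3 use that model, but none applies it to this analysis. The later SAP announced in Section 11, or a charter, could add the channel; the conflicting protocol sentences would remain.

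Three stronger inferences are tempting, and the documents do not support them.

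- *Type I error is inflated.* About 5.6% two-sided would result if the size went to 218 whenever conditional power is below 0.8. The if-and-only-if wording forbids that.
- *Nobody is assigned the analysis anywhere.* This can be said only of the available text. Administrative entries of Section 1, including 1.3 (Statistician), were not in it.
- *The board is safety-only.* Sections 11.3 and 12.2 give it efficacy stopping criteria. What they lack is the sample-size task.

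**Conclusion.** The point holds and should be fixed. Sections 11.2 and 12.2 give incompatible instructions on either reading of the decision sentence. On the broader reading, Section 11.2 also contradicts itself on whether the increase is binding. In the available text, no passage assigns the 82-patient conditional-power analysis or says what is communicated.

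The numerical effect is modest: the situation arises in about a sixth to a fifth of trials, at a cost of at most about 5 points of power. These figures rest on the assumed observed-trend formula and the unadjusted test, whereas the planned primary analysis is a logistic regression adjusted for baseline volume. The textual conflict depends on none of this.

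The main risk is operational: knowledge of the approximate interim effect among those leading recruitment. Blinded treatment and blinded reading of haematoma expansion (6.2 and 9.2.1) limit that risk but do not remove it.

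**What to change.** Amend Sections 11.2 and 12.2 together, with matching wording in 1.6 and 11.3:

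- State that the DSMB, with its statistician, performs the unblinded analysis of the first 82 patients and applies the prespecified rule: conditional power of 0.33 to 0.8 gives the smaller of the required size and 218; otherwise 109. Give the formulas for conditional power and required size.
- Replace the final-decision sentence. The CIs and steering committee receive only the board's recommended target size or a continue/stop recommendation, with no interim effect, conditional power or rates by arm. They keep the power to stop under Section 2.9 or on DSMB advice.
- State one outcome for a required size above 218, so that the cap and the discussion do not both apply.
- Schedule the analysis explicitly. Do not rely on the 80% meeting coinciding with it: reaching 82 from 87 recruited would need a drop-out figure stated only for 218, and Section 11.4 imputes missing outcomes.
- Use one name for the board and one recipient for its advice.

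The cost is one amendment and a charter line; the board already includes a statistician. The CIs and steering committee lose discretion over interim efficacy data. Leakage is reduced, not abolished, because an exact released size still allows back-calculation. Releasing only 109 or 218 would limit that, but it is optional, changes the prespecified rule and raises expected size from 117–119 to 128 (54% versus 27%) or from 120–122 to 133 (54% versus 35%).

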### 11.3 Statistical criteria of termination of trial

The DSMC will recommend to the TSC that the trial be stopped if there is proof beyond reasonable doubt (with a 99% CI) of overall benefit with the active treatment or if there is a lower level of evidence suggesting overall hazard. Evidence of hazard will include effect on the primary outcome (HE) and analysis of safety endpoints, as specified in the protocol (death, VTE, ischaemic events, seizures, serious adverse events).

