## 1.6 Data Safety Monitoring Board

The study will be terminated early in case of major safety concerns. For this purpose, a DSMB (Data-Safety-Monitoring-Board) will be installed. The DSMB will be independent of the sponsor, the CIs and competing interests. It will comprise of two experienced stroke neurologist or neuroradiologists and one statistician. The DSMB will meet after recruitment of 50% and 80% of the patients. It will monitor the frequency of the clinically important safety events. In case of serious safety concerns, the DSMB will alert the chief investigator in order to terminate the study.

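### Does the 99% CI benefit rule in section 11.3 need a fixed occasion, a named outcome and an adjusted final threshold?

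*Combined protocol and SAP*

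**What the plan says.** Section 11.3 has the committee recommend that the trial "be stopped if there is proof beyond reasonable doubt (with a 99% CI) of overall benefit with the active treatment". For hazard it accepts weaker evidence and adds: "Evidence of hazard will include effect on the primary outcome (HE) and analysis of safety endpoints". It gives no number or timing of looks and no benefit outcome.

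Section 11.2 schedules the one interim analysis of HE: "An interim analysis of the primary endpoint is performed using data from the first 82 patients". Its purpose is sample size. Conditional power is calculated and, "if it falls within the prespecified 'promising' range between 0.33 - 0.8", N is raised to restore 0.8, up to 218. Then: "The final decision to increase the sample size or stop the trial prematurely will be taken by the CIs and the steering committee". The 11.3 rule is not mentioned there.

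Section 1.6 sets the board's calendar and content: "The DSMB will meet after recruitment of 50% and 80% of the patients" and "It will monitor the frequency of the clinically important safety events". Section 12.2 describes the same two meetings as a "review of SAEs, in all patients; in case of concerns, unblinding will be requested", but goes on to have the board advise the chief investigators if it sees credible harm or very strong efficacy.

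The significance level is two-sided 0.05 (section 11.2), and the primary test is a logistic regression adjusted for baseline volume (section 11.4). Section 11 defers detail to a statistical analysis plan, to be written before the code is broken.

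**The concern.** A benefit rule needs an occasion, an outcome and someone holding the unblinded comparison. Section 11.3 supplies none of these. The meetings on the calendar review serious adverse events, so no between-arm interval for HE is planned there. The one planned HE comparison serves another purpose, and its decision goes to other people.

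Each extra chance to declare benefit adds false-positive probability, and the final 0.05 is not adjusted. If the rule could be read at several unspecified times, the stated level might not hold, and an early stop or a final p just under 0.05 could be contested.

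**Working it through.** **Inputs.** From 11.2: HE 54% vs 27%, N = 109, two-sided 0.05, 80% power, interim at 82, promising zone 0.33-0.8, cap 218. From 11.3: a 99% CI, taken as two-sided, so z = 2.576. From 1.6 and 12.2: meetings at 50% and 80%, about 55 and 87 of 109. Assumption: benefit is judged on HE, which 11.3 does not say.

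**1. The plan's N.** Per arm, pooled z-test, mean rate 0.405:

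n = [1.96·√(2·0.405·0.595) + 0.842·√(0.54·0.46 + 0.27·0.73)]² / 0.27² = 50.7, so 51 per arm and 102 in total.

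102/0.95 = 107.4, so 108. The stated 109 is reproduced closely if 5% dropout is allowed; 11.2 states that rate only for the 218 figure.

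**2. Timing.** 82/109 = 75.2%.

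**3. Promising zone.** With interim statistic z₁ and the observed trend continuing,

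CP = 1 − Φ{ (1.96·√109 − z₁·√82)/√27 − z₁·√27/√82 }.

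At z₁ = 1.510: (20.46 − 13.67)/5.196 − 0.867 = 0.440, so CP = 0.33. At z₁ = 2.063: 0.343 − 1.184 = −0.841, so CP = 0.80.

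**4. Is the plain final test safe after an increase?** The error-preserving critical value at new size N* is

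c = { √[(N* − 82)/27]·(1.96·√109 − z₁·√82) + z₁·√82 } / √N*.

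At z₁ = 1.510 and N* = 218: (2.244·6.79 + 13.67)/14.76 = 1.958, just below 1.960. At conditional power 0.32 it would be 1.967. The 0.33 limit therefore fits this design, and the increase is slightly conservative: with no benefit look the overall level is 4.85-4.89%.

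**5. Adding the benefit stop.** The trial rejects if Z > 2.576 at a look in the benefit direction or |Z| > 1.96 at the end. Under the null (joint normal statistics, integration and simulation):

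| HE read against the 99% rule | Increase followed | N stays at 109 |
|---|---|---|
| never | 4.85-4.89% | 5.00% |
| once, at 82 | 4.93-4.96% | 5.08-5.09% |
| at 50% and 80% | 5.13-5.18% | 5.26-5.27% |
| at 50%, 82 and 80% | 5.16-5.21% | 5.29-5.31% |

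Ranges cover independent runs and two ways of calculating the new N. In the benefit direction alone (nominal 2.5%), a single look at 82 gives 2.43-2.47% with the increase and 2.58% without. The worst row reaches 2.81%, with N at 109.

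**6. Other readings.** If 99% means a one-sided bound (z = 2.326), one look at 82 gives 5.13% with the increase and 5.27% without. With N at 109, that bound gives 5.69% for looks at 50% and 80% and 5.79% for all three. If crossings in the harmful direction also counted as rejections at z = 2.576, the N = 109 figures for those two schedules would be 5.54% and 5.61%. Section 11.3 attaches 99% to benefit only, and an unqualified 99% CI is normally two-sided, so the table is the natural reading.

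**7. Scale.** A binary check of an unadjusted Wald test with 54% HE in both arms puts the final test alone at 5.41%. That is not the planned adjusted test, but small-sample error of that order exceeds what any row of the table adds.

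**The case for a change.** The best case for a change is prespecification. As written, one cannot tell when the rule is read, on which outcome or from whose data. Section 11.3 sends the recommendation to the steering committee, while 1.6 and 12.2 send it to the chief investigators. Section 12.2 keeps both groups ignorant of interim results, yet 11.2 has them decide on the increase. Nor is the rule remote. With 41 per arm it needs an observed difference of about 2.576·√(2·0.405·0.595/41) = 0.279, close to the assumed 0.27, so under the design it would be met at 82 about half the time (45-51% by method). A sentence or two would settle this, and one reading at 82 costs no power (84.1-84.5% against 83.9-84.3% without it).

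The textual gap stands. Three things weaken the case for imposing a remedy:

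- It is too strong to say that no occasion exists. Section 12.2 attaches efficacy advice to the 50% and 80% reviews; what is missing is a statement that HE is tabulated there.
- Fixing the reading at 82 does not guarantee 5%, because the increase is discretionary. Nor does it always coincide with the 80% meeting: 0.8·109 = 87, but 0.8·218 = 174, some 92 patients after the interim.
- A final threshold of 0.047 with looks at 50% and 80% brings the two-sided total to 4.86-4.98%, yet across the extra-look schedules it leaves the benefit tail at 2.55-2.67%, still above 2.5%.

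Making HE the sole basis for a benefit stop would also settle a question the plan leaves open. Section 11.3 speaks of benefit overall, and section 4.2 calls HE a surrogate. Reasonable statisticians would differ on that.

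**Conclusion.** No change to the plan is called for. Section 11.3 is short on detail and sits loosely with 1.6, 11.2 and 12.2, but the consequence for the final test is slight: 4.93-4.96% with one HE reading at 82 and the increase followed, about 5.08% if N stays at 109, and at most about 5.3% with HE read at all three points. The excess over 5% is therefore no more than about 0.3 points.

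This rests on a two-sided 99% interval, benefit judged on HE, the normal approximation, and every crossing treated as a stop. The last makes the figures upper bounds for an advisory rule. A one-sided 99% bound read at all three points with N fixed would give 5.79%, but that is not the ordinary meaning of the text.

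Occasion, outcome and recipients of the unblinded comparison are what analysts settle in the analysis plan that section 11 promises. Any sensible choice there leaves the conclusions of the trial essentially as they are.

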### 11.4 Planned Analyses

Analysis will be by intention-to-treat; Missing outcome data will be imputed assuming worst possible outcome.

The primary outcome (HE) is to be compared between treatment and control arms adjusted for baseline volume using binary logistic regression. Although both baseline covariate adjusted and unadjusted results will be reported, baseline covariate adjusted analysis is prespecified as the primary outcome analysis for this trial.

As secondary outcome analyses, the proportions of mRS 0–4, mRS 0–3, and mortality outcomes will be compared between active and placebo arms of the trial adjusted for baseline volume using a binary logistic regression model. Analysis of the categorical shift in mRS will also be undertaken on the full range of the mRS using the Cochran–Mantel–Haenszel shift test and proportional odds logistic regression, subject to the validity of shift analysis model assumptions. Other secondary outcome analyses will be carried out according to standard statistical principles for comparison of parametric or nonparametric distributions as appropriate.

Exploratory analysis will be run on the primary and secondary outcomes, with adjustments for baseline

variables such as age, Glasgow coma scale (GCS), presence of IVH, and ICH location, and in the following subgroups: onset-to-treatment time (<six vs. >six-hours), baseline ICH volume (<30 vs. >30 ml), anatomical location (deep, lobar, or cerebellar), IVH (absent vs. present), GCS (>12 vs. 8–12), and age (<70 vs. >70), presence of spot-sign. These analyses will be hypothesis generating, as the trial is not powered for them.

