## STUDY SUMMARY IN LOCAL LANGUAGE

Neue, direkte, nicht Vitamin-K antagonistisierende orale Antikoagulantien (NOAC oder DOAC) sind wirksame Medikamente zur Prophylaxe und Behandlung einer Vielzahl von thrombembolischen Erkrankungen wie zum Beispiel der Hirnschlagprophylaxe bei Patienten mit Vorhofflimmern. Die gefürchtetste Komplikation einer NOAC-Behandlung ist eine Hirnblutung (=intracerebral hemorrhage, ICH). Hirnblutungen bei Patienten unter Antikoagulantienbehandlung (alte Antikoagulantien wie Vitamin K-Antagonisten oder NOAC) weisen häufig Nachblutungen (=Hämatomexpansion, HE) in der Frühphase nach dem Ereignis auf, welche ein schlechter prognostischer Faktor sind. Insgesamt ist die Prognose bei Patienten mit Hirnblutungen unter Antikoagulantien schlecht mit einer hohen Sterblichkeit (ca. 20%) sowie einer hohen Rate an Patienten mit dauerhafter neurologischer Behinderung. Seit kurzem existieren sogenannte Antidots gegen NOAC, jedoch gibt es keine evidenz-basierte Behandlung der NOAC-Hirnblutung, welche nachweislich das klinische Outcome verbessern und Nachblutungen verhindern kann.

Tranexamsäure ist ein seit > 20 Jahren bekanntes Medikament, dass in vielen Bereichen der Medizin zur Stillung von Blutungen, zum Beispiel nach Unfällen oder während Operationen, eingesetzt wird. Aktuell wird in einer grossen, multi-nationalen Studie die Wirkung von Tranexamsäure bei Patienten mit spontanen Hirnblutungen (Patienten, die keine Antikoagulantien/NOAC eingenommen haben) erforscht (TICH-2 Studie).

In der vorliegenden Studie möchten wir in einer Studie an mehreren Zentren die Wirkung von Tranexamsäure im Vergleich zu Placebo zusätzlich zur medizinischen Standardbehandlung (welche unter Umständen Antidots beinhalten kann) bei Patienten mit NOAC-Hirnblutungen testen. Das primäre Ziel ist es, die Rate an HE 24 Stunden nach Aufnahme zu reduzieren. Sekundäre Ziele ist eine Reduktion von Tod und neurologischer Behinderung nach 3 Monaten.

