### **5.2 Secondary Outcomes**

Secondary outcome measures are

- (I) modified Rankin Scale (mRS) 0–4 at three-months;
- (II) mRS 0–3 at three-months;
- (III) Categorical shift in mRS at three-months;
- (IV) Absolute ICH growth volume by 24 ± 3 hours, adjusted for baseline ICH volume;
- (V) Symptomatic HE defined as HE and neurological deterioration of NIHSS >4 points or GCS >2 points
- (VI) Death due to any cause by three-months;
- (VII) major thromboembolic events (myocardial infarction, ischemic stroke, pulmonary embolism – safety endpoints)
- (VIII) NCH intervention (including craniectomy, EVD, hematoma evacuation)
- (IX) In-hospital mortality

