### 7.4 Criteria for withdrawal / discontinuation of participants

Participation in the trial is voluntary and patients are free to withdraw from the trial at any stage without

giving a reason. Study medication may be stopped at any time by the investigators or any treating clinician if deemed in the patient's best interest. Treatment (with tranexamic acid/placebo) will be given on top of 'best medical care'. Participants may be withdrawn from the trial either at their own request or at the discretion of the Investigator. The participants will be made aware that this will not affect their future care. Participants will be made aware (via the information sheet and consent form) that should they withdraw the data collected to date cannot be erased and may still be used in the final analysis. Enrolled participants who withdraw before randomisation can be replaced (though keeping their trial ID), but participants who withdraw after randomisation will not be replaced.

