## 10. SAFETY

During hospitalisation in the participating center until day 7, all adverse events (AE) and all serious adverse events (SAEs) are collected, fully investigated and documented in source documents and case report forms (CRF). After discharge from the participating hospital and/or day 7 (what occurs first), only study outcome events (death, ischemic vascular events) are collected as SAE until end of study. Study duration encompassed the time from when the participant signs the informed consent until the last protocol-specific procedure has been completed.

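### The worst-outcome rule for missing data is not limited by endpoint: read literally it turns unknown status into deaths and thromboembolic events, gives no value for ICH growth, and no sensitivity analysis checks it

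*Combined protocol and SAP*

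**What the plan says.** Section 11.4 (Planned Analyses) sets the analysis as intention-to-treat and gives one rule for missing data: "Missing outcome data will be imputed assuming worst possible outcome". No endpoint is named or excluded. Efficacy is not separated from harm, nor binary outcomes from continuous ones.

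The outcomes in section 5.2 include three-month death, in-hospital mortality, "major thromboembolic events (myocardial infarction, ischemic stroke, pulmonary embolism" (labelled there as safety endpoints) and "Absolute ICH growth volume by 24 ± 3 hours, adjusted for baseline ICH volume". Section 11.4 plans that "mortality outcomes will be compared between active and placebo arms of the trial adjusted for baseline volume", by binary logistic regression. Thromboembolic events and ICH growth are left to standard methods.

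Under section 7.4, "participants who withdraw after randomisation will not be replaced", so these patients stay in the intention-to-treat set. Section 11 says that a detailed SAP will be written before the code is broken. No such text is in the documents, and nothing says that it will narrow the rule.

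**The concern.** Worst-outcome imputation is usually chosen because it is cautious for efficacy. For a harm endpoint it is not. Adding the same share of invented events to both arms dilutes a real excess on the active drug, and sections 3.2.6 and 3.4 themselves list thromboembolic events as a possible risk of tranexamic acid. If missingness differs between arms, the invented events differ too, and the comparison can move either way.

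There are two further gaps. Absolute ICH growth is continuous and has no stated maximum, so the rule yields no number for it. And for HE and mRS the verdict rests on one imputation assumption. The adjusted, unadjusted, covariate and subgroup analyses in section 11.4 all leave that assumption unchanged.

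**Working it through.** **Inputs from the documents.** HE 54% under placebo, 27% under TA at 109 patients, 35% under TA at 218, two-sided 0.05 (section 11.2); 1:1 allocation (section 6.2.1). Drop-out of 5% is stated only for the 218-patient case: "assumed a drop-out rate of 5 % and an incidence rate of 54 % under placebo". Mortality is about 20%, from the German summary: "hohen Sterblichkeit (ca. 20"%.

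**Assumptions.** The documents give no missing rate for harm outcomes, no thromboembolic rate and no harm ratio. I use 1%, 2% and 5% missing, a death ratio of 1.5, and thromboembolic rates of 3% (placebo) and 6% (TA).

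**Design figure first.** Power = Φ[(d√n − 1.96√(2p̄(1−p̄))) / √(p₁(1−p₁)+p₂(1−p₂))], n per arm, with 5% lost:
- 109 patients, n = 54.5 × 0.95 = 51.8: (1.943 − 1.361)/0.667 = 0.872, power 80.8%.
- 218 patients, n = 109 × 0.95 = 103.6: (1.933 − 1.378)/0.690 = 0.806, power 79.0%.

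Both are close to the stated 80%, so these inputs are a fair setting for the HE check below.

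**Harms, equal missingness m.** The imputed rate is p′ = p + m(1 − p). The difference becomes (1 − m)(p₂ − p₁), so it shrinks by exactly the missing share.

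| Missing per arm | Death, 20% vs 30% (ratio 1.5) | Thromboembolic, 3% vs 6% (ratio 2.0) |
|---|---|---|
| 1% | 20.8% vs 30.7%, ratio 1.48 | 4.0% vs 6.9%, ratio 1.75 |
| 2% | 21.6% vs 31.4%, ratio 1.45 | 4.9% vs 7.9%, ratio 1.60 |
| 5% | 24.0% vs 33.5%, ratio 1.40 | 7.9% vs 10.7%, ratio 1.36 |

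The rarer the event, the stronger the dilution. At 5% missing, about 109 × 0.05 = 5.5 patients would be counted as events, against 109 × 0.03 = 3.3 expected real events at the 3% rate.

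**Harms, unequal missingness (assumed 2% vs 8%).**
- No true effect, thromboembolic 3%: 0.03 + 0.02 × 0.97 = 4.9% vs 0.03 + 0.08 × 0.97 = 10.8%, a spurious 5.8 points. The chance of p < 0.05 is about 20% at 109 and 36% at 218.
- No true effect, death 20%: 21.6% vs 26.4%, a spurious 4.8 points; about 9% and 13%. (Normal approximation, rough for rare events.)
- True 3% vs 6%, with 8% missing on placebo and 2% on TA: 0.03 + 0.08 × 0.97 = 10.8% vs 0.06 + 0.02 × 0.94 = 7.9%. The real excess on TA is hidden and the sign reverses.

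**HE.** I simulated 400,000 trials per setting with a pooled z-test and missingness equal by arm and unrelated to HE, and compared the observed-only verdict with the worst-outcome verdict.

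| Missing | Verdicts differ, 109 patients | Verdicts differ, 218 patients |
|---|---|---|
| 2% | 3.6% | 3.5% |
| 5% | 6.2% | 6.3% |
| 10% | 9.7% | 9.7% |

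At 5% missing, about 70% of the disagreements are significance lost under the worst-outcome rule. With no true effect (54% in both arms), the verdicts differ in about 1.8–1.9% of trials and the false-positive rate stays near 5% (4.8–5.3%).

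**ICH growth.** No arithmetic applies: without a maximum there is no worst value to insert.

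**The case against.** The strongest reply is that little will be missing. Section 10 says that after discharge or day 7 "only study outcome events (death, ischemic vascular events) are collected as SAE until end of study". A reader might infer from this that harm data become sparse after the first week. It shows the reverse, since death and ischaemic vascular events are the ones still collected. Section 9.2.3 records thromboembolic events at each visit, section 9.2.3.1 has fatal events and listed vascular events reported to day 90, and section 9 allows a telephone interview with a relative or carer. In-hospital mortality can hardly be missing. What remains is withdrawal or loss to follow-up, which should be uncommon. This limits the size of the problem but does not remove it.

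Second, no sentence says that unknown status becomes an infarction or an embolism, and the later SAP could settle the scope. True, but the rule as it stands has no limit, and no text commits the SAP to adding one.

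Third, the rule mostly errs conservatively for HE, and a missing 24-hour scan may reflect early deterioration, in which case the worst outcome may be near the truth. That stands. It is a reason to keep the rule for HE and to test it.

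Fourth, a reader might infer that the 218-patient power is overstated, because the stated 80% fits drop-outs leaving the analysis whereas section 11.4 keeps them. The documents do not state that convention. For the total at 5% drop-out, the unpooled formula gives 217.8 for the 218 but 101.0 for the 109; the pooled formula gives 106.7 and 223.6. Neither clearly fits both. These figures also ignore the adaptive, covariate-adjusted design. No restatement of power is warranted.

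**Conclusion.** The point holds as one about scope and an unchecked assumption. As written, the rule covers death and thromboembolic events, where it is not conservative, and ICH growth, where it cannot be carried out. It is also the only missing-data assumption behind the HE and mRS results.

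The expected size is modest. For death, a ratio of 1.5 falls to between 1.48 and 1.40. For rarer thromboembolic events the relative distortion is larger. These figures rest on assumed missing rates, ratios and a thromboembolic rate that the documents do not give. The direction toward no difference holds only when missingness is similar in both arms. For HE, about 6% of trials change verdict at 5% missing, if missingness is unrelated to HE and the design effect is true.

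A reader might infer that the rule biases the primary result in favour of TA, or that it undermines the DSMB's safety review. Neither is supported. With equal missingness the HE error is mostly conservative, and the review in section 12.2 is of SAEs, not of imputed outcomes.

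**What to change.** In section 11.4, or in the SAP before the code is broken:

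1. Limit worst-outcome imputation to HE and mRS.
2. Analyse mortality and thromboembolic events among patients with known status without imputing events, keeping the planned logistic regression for mortality. Report the number of unknowns by arm. Because this departs from the full randomised set, add a sensitivity analysis that counts unknowns once as event-free and once as events.
3. State that an mRS imputed as 6 is not counted as a death.
4. Exclude absolute ICH growth from the rule, or assign a worst rank and analyse by ranks.
5. Add a multiple-imputation sensitivity analysis for HE and mRS, using arm, baseline variables and the day-7 and discharge mRS already in the section 9.1 schedule.

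The cost is a few sentences and a little more analysis work. No new data, visits or patients are needed, and the primary analysis of HE is unchanged.
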